Based Primary Care, and inpatient and outpatient rehabilitation settings. Potential Veterans with whom we have a treatment relationship will be pre-screened through standardized chart review followed by standardized phone screen. If eligible and interested in participating, Veterans will provide informed consent and be enrolled in the study; once enrolled, they will be randomized to either a waitlist control (GROUP2) or experimental (GROUP1) group. Participants will complete surveys and direct observation (Aims 1 & 2). Veterans will also undergo performance-based assessments of physical activity and physical function and complete self-reported measures for physical function, quality of life, loneliness, social support, and mental health.

Formal Inclusion/Exclusion Criteria

Inclusion

- ≥ 60 years of age
- Multiple chronic conditions (Functional Comorbidity Index⁶⁸ ≥ 3)
- Impaired physical function (≤ 10 on 30 second sit to stand)

Exclusion

- Life expectancy < 12 months
- Acute or progressive neurological disorder (e.g., Amyotrophic Lateral Sclerosis, recent stroke)
- Moderate to severe dementia without caregiver assistance (< 18 on telephone Montreal Cognitive Assessment (T-MoCA)⁶⁹)
- Unstable medical condition precluding safe participation in progressive rehabilitation (e.g., unstable angina) as defined by ACSM guidelines

We plan to randomize 50 Veterans (25 randomized to each group), with the goal of having 40 Veterans complete the study (20% attrition rate). Due to our enrollment process, we plan to have 70 Veterans sign the informed consent; this will allow for up to 20 Veterans to complete evaluation but be found ineligible based on identified exclusion criteria. The goal of the study is to obtain a representative sample of older Veterans at risk for, or presenting with, impaired physical function contributing to fall risk, physical dependence, and risk for hospitalization. Both sexes and all races are included in the study, however the Veteran population is predominantly male and Caucasian, which will be reflected in the enrollment.

D. Study Design and Research Methods

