Aim 2: Preliminary responses to the interventions will be determined via performance-based and self-report measures. Physical activity behavior outcomes (hypothesis 2) will include average 7-day step count (accelerometry; primary), self-efficacy (Self-Efficacy for Exercise Scale²) and exercise readiness to change (Exercise Stages of Change).⁷⁰ Physical function outcomes will include 30 second sit to stand test,³ arm curl test,⁷² 2-minute step test,⁷² and self-report Activity Measure for Post-Acute Care (AM-PAC).¹⁵ Social isolation and loneliness outcomes will include 3-Item Loneliness Scale¹⁷ and the Berkman Social Disengagement Scale.¹ The PROMIS-29 v2.0¹⁶ will measure quality of life (summative score), social support (subscale), and mental health (subscale). In addition, descriptive measures will be collected at baseline including demographics, medications, cognition (T-MoCA⁶⁹), depression (Patient Health Questionnaire-9 for depression⁷³), anxiety (General Anxiety Disorder-7⁷⁴), Mobile Device Proficiency Questionnaire-16,⁷⁵ and comorbidities (Functional Comorbidity Index⁶⁸).

ActiGraph physical activity monitors (ActiGraph Inc. Pensacola FL) will be used to obtain an objective measure of physical activity (PA). ActiGraph activity monitors assess PA using accelerometry, which allows objective evaluation of the relative volume (steps/day) and intensity (activity counts) of physical activity with high validity and reliability.⁷⁶⁻⁷⁸ Each participant will wear the ActiGraph for 10 days at the beginning and end of their intervention window (baseline and week 12 for GROUP1, week 12 and week 24 for GROUP2). The ActiGraph monitor will be used only for outcome data (not intervention) and provides no feedback to participants.

E. Description, Risks and Justification of Procedures and Data Collection Tools:

Potential Risks (Aim 1 and Aim 2)

Study Intervention and Assessments

We anticipate no greater risk than the minimal risk associated with standard telerehabilitation for Veterans participating in this study. All interventions and assessments are considered a part of physical therapy clinical practice. Because a physical therapist is not physically present with the participant during sessions, there is an increased risk for falls compared to in-person rehabilitation. Exercise is associated with inherent risks including muscle soreness, muscle strain, shortness of breath, and cardiac events. Precautions will be taken to minimize risks as follows:

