Heterogeneity of medically complex older adults: Medically complex older adults are heterogeneous in age, cognitive status, medical status, psychological comorbidity, living environment, and social support.²² Additionally, they experience acute exacerbations of chronic conditions impacting their response to treatment and contributing to high drop-out rates among this population. To accommodate for this from our experiences, we anticipated a higher attrition rate (20%) and adjusted enrollment accordingly.

G. Data Analysis Plan:

Analysis Plan. Analyses will be performed in SAS v 9.4 or above and hypothesis tests will be two-sided, assuming an alpha level of 0.05. Participant characteristics and outcome variables will be summarized using means, standard deviations (SD), medians, ranges, N and percent, as appropriate.

Aim 1. The percent of Veterans (1) achieving $\geq 80\%$ adherence and (2) scoring $\geq 4/5$ on the Acceptability of Intervention Measure will be calculated with associated 95% exact binomial confidence intervals. We will additionally calculate the proportion of adverse events that are found to be possibly, probably, or definitely related to the intervention.

Aim 2. Given the small samples, the median change from baseline to 12 weeks for those randomized to the intervention will be compared between the groups using a Wilcoxon rank-sum test for each outcome of interest (7-day average step count as primary). Estimates of variability (SD) in the change from pre to post-intervention for the pooled sample completing the intervention (N=40) will be calculated for each outcome and reported with 95% CIs. These estimates and the CIs will inform sample size calculations for a future effectiveness trial.

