The VA has established rehabilitation programs for inpatient, home, and outpatient settings, but these typically require in-person attendance, address one area of functional impairment, and under-dose the intensity of rehabilitation. Further, Veterans often face barriers to attending in-person appointments; for example, living in rural locations, lack of transportation, or limited social support. As a result, many Veterans continue to have residual physical function limitations that prevent them from participating in life roles, navigating their home and the community, and participating in continued rehabilitation exercises in the community setting. It is unclear how telehealth strategies could be effectively and safely utilized to provide rehabilitation services to Veterans who lack access to these important services. Indeed, telehealth platforms offer a solution to overcome access barriers (rurality, transportation), but no current research applies telerehabilitation to medically complex older Veterans.

The current study will assess the feasibility, acceptability, and safety of the multi-component rehabilitation program for high risk, high need Veterans with multiple comorbidities and functional deficits. Additionally, response to the multicomponent telerehabilitation program will also be measured to determine preliminary effectiveness. Study findings will guide refinement of telerehabilitation methods, so they are effective, easily implemented, and safe. This study will provide critical insight for providers regarding telerehabilitation for medically complex older Veterans and its utilization to improve physical function and concurrently reduce the impact of social isolation.

I. References:

1. Department of Veteran Affairs Office of Rural Health. Rural Veterans. <https://www.ruralhealth.va.gov/aboutus/ruralvets.asp>. Published 2020. Accessed July 15, 2020.

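### The Aim 2 group comparison plans a Wilcoxon test with no between-group difference or 95% CI, and for step count it cannot be computed on the ActiGraph schedule as written

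*Combined protocol and SAP*

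**What the plan says.** Section G (Data Analysis Plan), Aim 2, sets the between-group analysis: "Given the small samples, the median change from baseline to 12 weeks for those randomized to the intervention" is to be "compared between the groups using a Wilcoxon rank-sum test for each outcome of interest (7-day average step count as primary". Tests are two-sided at 0.05. The plan's general descriptive sentence reads "Participant characteristics and outcome variables will be summarized using means, standard deviations (SD), medians, ranges, N and percent, as appropriate". The 95% intervals named in Section G are exact binomial intervals for the Aim 1 percentages and intervals for the SD of change: "Estimates of variability (SD) in the change from pre to post-intervention for the pooled sample completing the intervention (N=40", to size a later trial. No interval is named for a difference between the groups.

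Section H gives the purpose: "response to the multicomponent telerehabilitation program will also be measured to determine preliminary effectiveness".

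The schedule for the primary Aim 2 outcome is not consistent:

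- Sections I (Hypotheses and Specific Aims) and D list outcome assessment at baseline, 6, 12 and 24 weeks without limiting it by group.
- The ActiGraph paragraph under Outcomes in Section D ties wear to each participant's own intervention window: "baseline and week 12 for GROUP1, week 12 and week 24 for GROUP2".
- Section F (lack of long-term follow-up) expects to compare GROUP1 activity at 24 weeks with week 12 and baseline. The ActiGraph paragraph schedules no 24-week wear for GROUP1.

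**The concern.** Two things are at issue.

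First, the randomized comparison ends in a test. A p-value with separate group summaries does not state how large the difference between the groups may be, or how precisely it was estimated. In a pilot of this size a non-significant result could mean little response or too few data, and only an interval for the difference separates the two. The baseline and week-12 values needed for an adjusted estimate are collected for the other outcomes, but no such estimate is planned.

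Second, for step count the planned quantity does not exist in one arm if the ActiGraph paragraph governs. Without a GROUP2 baseline, the Wilcoxon test on change, a Hodges-Lehmann difference in change and an ANCOVA all fail for the same reason. Substituting GROUP2's change from week 12 to week 24 would compare two treated periods, and the control comparison would be lost.

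**Working it through.** **1. The plan's own figure.** The population section randomizes 50 (25 per group) "with the goal of having 40 Veterans complete the study (20% attrition rate". 50 × (1 − 0.20) = 40, and 40 / 0.80 = 50. The figure reproduces and gives about 20 completers per arm. No power is stated for Aim 2.

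**2. Can the step-count test be computed?** Section G needs baseline and week 12 in both groups.

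| Group | Wear listed in the ActiGraph paragraph | Baseline to week-12 change available |
|---|---|---|
| GROUP1 | baseline, week 12 | yes |
| GROUP2 | week 12, week 24 | no (0 of 25) |

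Only the week-12 value is then common to both arms. If the general schedule in Sections I and D governs instead, the change is available in both. The documents do not say which applies.

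**3. Precision with 20 per arm.** SD means the outcome SD at one visit, assumed equal at baseline and week 12. The documents give no baseline to week-12 correlation r, so a range is assumed. With t(0.975, 38) = 2.024:

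- Week-12 value alone: 2.024 × √(2/20) = 0.64 SD.
- t interval on change: 0.64 × √(2(1 − r)).
- ANCOVA, approximately: 0.64 × √(1 − r²).
- Hodges-Lehmann on change: the 128th and 273rd of the 400 ordered pairwise differences (exact tail 0.0245). The simulated half-width is 0.65 SD of the change with about 95% coverage, and this is multiplied by √(2(1 − r)).

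| 95% CI half-width (SD) | r = 0.5 | 0.7 | 0.8 | 0.9 |
|---|---|---|---|---|
| Week-12 value only | 0.64 | 0.64 | 0.64 | 0.64 |
| t interval on change | 0.64 | 0.50 | 0.40 | 0.29 |
| Hodges-Lehmann on change | 0.65 | 0.51 | 0.42 | 0.29 |
| ANCOVA | 0.55 | 0.46 | 0.38 | 0.28 |

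(Scaling gives 0.41 for Hodges-Lehmann at r = 0.8; direct simulation gives 0.42.)

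**4. What the interval adds.** With an assumed true effect of 0.3 SD (10,000 simulated trials), 85%, 79%, 70% and 49% of trials are non-significant at the four values of r. Of those, 83%, 74%, 59% and 15% have an interval that still includes 0.6 SD. At r = 0.7 the median limits in the non-significant trials are −0.28 and 0.74 SD.

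**5. What adjustment adds.** Assumed effect 0.6 SD, normal data. For the t-test on change the noncentrality is 0.6 / (√(2(1 − r)) × √(2/20)) = 1.90, 2.45, 3.00 and 4.24.

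| Power (%) | r = 0.5 | 0.7 | 0.8 | 0.9 |
|---|---|---|---|---|
| Wilcoxon on change | 43 | 64 | 81 | 98 |
| t-test on change | 46 | 66 | 83 | 98.5 |
| ANCOVA | 56 | 72 | 86 | 99 |

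ANCOVA minus the t-test is about 10, 6, 3 and 0 points. The larger gap to the Wilcoxon mixes adjustment with the choice of ranks or means.

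**6. Scale.** Lognormal data (assumed log SD 0.6), Wilcoxon on change / ANCOVA:

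- Multiplicative effect, untransformed ANCOVA: 45/48, 64/62, 81/76, 97/95. It loses about 2 to 5 points at r of 0.7 or more.
- Additive effect, untransformed ANCOVA: 58/59, 78/73, 91/84, 99/97. It loses 2 to 7 points at r of 0.7 or more.
- Multiplicative effect, log-scale ANCOVA: 45/56, 64/72, 81/86, 97/99.

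**The case against.** The strongest reply is that this is a feasibility pilot. Hypothesis 2 is a within-participant trend from program start to program end, plus SDs for sizing the next trial. Means and SDs will be reported and, if given by group, would let a reader build an approximate interval for a mean difference. The rank test is a reasonable choice at this size, and the plan gives its reason. Most of this stands, and it is why the point is small. But Section G itself makes the randomized comparison a test on every outcome, and an interval that readers must assemble is not a planned one.

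It also stands that an ANCOVA for every outcome would be excessive. Many are counts or bounded scores that the continuous simulations fit poorly. Sit-to-stand is admitted at 10 or less with no lower limit, so zeros are possible and a log ratio would be undefined.

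Four stronger readings are tempting and not supported:

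- That the Wilcoxon test is invalid or should be replaced. As a method it is sound wherever both arms have a baseline, and untransformed ANCOVA can do worse on skewed data.
- That most plausible effects will be non-significant. The documents name no plausible effect. In step 5 the Wilcoxon detects a 0.6 SD effect in 64% to 98% of trials at r of 0.7 or more.
- That GROUP2 will certainly lack a baseline step count. The sections conflict, and the general schedule lists a baseline.
- That the planned SD is inadequate for sizing the next trial. It suits a trial analysed on change, and its own 95% CI at N = 40 is already 0.82 to 1.28 times the SD, from √(39/χ²) at the 0.975 and 0.025 quantiles.

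**Conclusion.** The point holds in two parts. Section G plans no between-group difference with a 95% CI and no baseline-adjusted estimate for Aim 2; that follows from the text. For step count, the planned test cannot be computed under the ActiGraph paragraph, and that paragraph conflicts with Sections I, D, F and G. Section G's sentence also names only those randomized to the intervention while describing a comparison of two groups.

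The half-widths and power figures rest on 20 completers per arm and on assumed correlations, effect sizes and distributions. The gain from adjustment is modest and falls to nothing at high correlation; on the wrong scale it turns into a loss. The consequence for this pilot is minor, and the change is worth considering rather than essential. Reconciling the step-count schedule comes first, because the primary Aim 2 comparison depends on it.

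**What to change.** 1. Reconcile Sections I, D (general schedule and ActiGraph paragraph), F and G so that step count has a baseline in both groups. Otherwise, define the randomized contrast as the week-12 step count with its CI, accepting the first row of the precision table. Reword the Aim 2 sentence in Section G so that it names both groups.
2. Keep the Wilcoxon test. For each outcome with a baseline in both groups, report beside it the Hodges-Lehmann difference in change with 95% CI. For short ordinal scales such as Exercise Stages of Change, report instead the probability that a GROUP1 change exceeds a GROUP2 change, with CI.
3. As a supporting analysis, at least for step count, give the ANCOVA of the week-12 value on group and baseline with 95% CI. Fix the scale in advance, and use logs only for right-skewed outcomes without zeros.

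Cost: a few sentences in Section G and a little more SAS work. The intervals need no new data. New data arise only if reconciliation adds baseline ActiGraph wear in GROUP2. The ANCOVA costs one degree of freedom and assumes a linear, common slope on the chosen scale.

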Engaging Medically Complex Veterans in Tele-Rehabilitation Using a Biobehavioral Approach: A Pilot Study of Feasibility and Acceptability

NCT04942613

July 14, 2022

COMIRB Protocol

COLORADO MULTIPLE INSTITUTIONAL REVIEW BOARD
[name] [contact] [contact]

Protocol #: 21-2773

Project Title: Engaging Medically Complex Veterans in Tele-Rehabilitation Using a Biobehavioral Approach: A Pilot Study of Feasibility and Acceptability

Principal Investigator: [name] [name]

Version Date: 07.14.2022

I. Hypotheses and Specific Aims:

This is a single-site, randomized pilot study using a two-group (GROUP1 and GROUP2) crossover design. Fifty Veterans with medical complexity and deficits in physical function will participate. Outcomes will be assessed at baseline (pre-intervention), 6 weeks (intervention mid-point), 12 weeks (end of intervention), and 24 weeks.

AIM 1: To determine the feasibility and acceptability of a multicomponent telerehabilitation program.

Hypothesis 1a: 75% of Veterans will achieve $\geq 80\%$ adherence as measured by attendance.

Hypothesis 1b: At least 75% of Veterans will perceive the program as acceptable ($\geq 4/5$ on Acceptability of Intervention Measure¹³) and feasible ($\geq 4/5$ on Feasibility of Intervention Measure). In addition, we will monitor adverse events and categorize severity (mild, moderate, severe) and relatedness (definitely, probably, possibly).

AIM 2: To assess the preliminary response of a multicomponent telerehabilitation using a two-group randomized crossover design and determine variability estimates. Outcomes for this aim are accelerometer-based physical activity, physical function, quality of life, and loneliness.

Hypothesis 2: At program end (GROUP1 12 weeks, GROUP2 24 weeks), participants will have a trend of improved outcomes (accelerometer 7-day average step count with ActiGraph physical activity monitors (ActiGraph Inc. Pensacola FL, primary) compared to program start (GROUP1 baseline, GROUP2 12 weeks). In addition, using the pooled intervention sample, variability estimates (standard deviation), will be determined for change in physical activity, physical function (,30 second sit to stand¹⁴) and self-report measures of physical function (Activity Measure for Post-Acute Care¹⁵), quality of life (PROMIS 29 Profile v2.0¹⁶), and loneliness (3-item loneliness scale¹⁷ Berkman Social Disengagement Scale¹). This will allow for sample size estimates for the subsequent larger effectiveness trial.

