This new line of research builds on the collective experience of the investigative team. The PI and Co- Investigators have worked together over the past 7 years to 1) develop progressive rehabilitation strategies for medically complex patients (VA RR&D I21 RX002054, VA RR&D I01 RX001978), 2) develop and test biobehavioral strategies to improve physical activity for patients following dysvascular lower limb amputation⁸ and total knee arthroplasty,⁹ and 3) test and refine telerehabilitation delivery for patients following total knee arthroplasty (NIA R44 AG055341). This study will be the first to combine these lines of research into a coherent multicomponent program. Further, this is the first study to determine the safety and feasibility of telerehabilitation approaches for a high-risk, medically complex population. The investigative team's collective experience and ongoing work in these areas positions them uniquely to lead the proposed investigation.

IV. Research Methods

C.1 Outcome Measures:

Aim 1: Feasibility outcomes provide information to help determine if a larger study should be performed. Feasibility includes adherence, acceptability, and safety, and satisfaction. Additional factors may influence feasibility, and the following surveys for will be assessed

at program end for Veterans and therapists: Feasibility of Intervention Measure,¹³ Acceptability of Intervention Measure,¹³ Intervention Appropriateness Measure.¹³ Satisfaction is measured by V-signals which is a survey specific to the VA; it measures satisfaction associated with telerehabilitation services. Additionally, we will monitor recruitment rate (proportion of Veterans enrolled out of those screened) and retention (proportion of Veterans who complete program out of all enrolled) to inform feasibility of a larger randomized controlled trial for effectiveness.

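### The listed ActiGraph wear windows give GROUP2 no baseline step count, so the planned between-group comparison on the primary Aim 2 outcome cannot be run unless the schedule is reconciled

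*Combined protocol and SAP*

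**What the plan says.** Section G (Data Analysis Plan, Aim 2) has two parts. The first is a Wilcoxon rank-sum test for each outcome, step count being primary: "the median change from baseline to 12 weeks for those randomized to the intervention will be compared between the groups". The second is the variability estimate for sizing the next trial: "Estimates of variability (SD) in the change from pre to post-intervention for the pooled sample completing the intervention (N=40) will be calculated". Hypothesis 2 in Section I describes the same estimate as "using the pooled intervention sample, variability estimates (standard deviation), will be determined for change in physical activity".

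Section D (Outcomes, Aim 2) gives the only dates for ActiGraph wear. Each Veteran wears the monitor for 10 days at each end of the intervention window: "baseline and week 12 for GROUP1, week 12 and week 24 for GROUP2".

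The general schedule in Section I makes no distinction between groups: "Outcomes will be assessed at baseline (pre-intervention), 6 weeks (intervention mid-point), 12 weeks (end of intervention), and 24 weeks". The opening paragraph of Section D likewise includes a baseline collection without exempting GROUP2. Section F (on long-term follow-up) expects to compare GROUP1's activity at 24 weeks with its week-12 and baseline levels.

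Section C.1 describes the next study as a randomized trial; recruitment and retention are monitored "to inform feasibility of a larger randomized controlled trial for effectiveness".

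**The concern.** A between-group test of change from baseline to week 12 needs both measurements in both groups. For GROUP2 that interval is the waitlist period, and the wear list starts GROUP2 at week 12. Staff who follow the list would collect no GROUP2 baseline step count, and a missed baseline cannot be recovered later. The pilot would then lose its only randomized comparison on the outcome it names as primary.

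A smaller matter concerns sizing. The variance in a two-arm trial comes from both arms, but the planned SD describes intervention periods only. Section G plans general SD summaries of the outcome variables, but it does not name an SD of change over the waitlist period, which is the pilot's only control period.

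**Working it through.** **Inputs.** 50 randomized, 25 per group, with 20% attrition (population section under Section IV); wear dates from Section D; analyses from Section G; windows from Hypothesis 2.

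**1. The plan's own figure.** 50 × (1 − 0.20) = 40, which reproduces the N=40 in Section G. If attrition is equal in the two groups (an assumption), that is 20 per group.

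**2. Step-count data needed against wear listed.**

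- GROUP1, baseline to week 12: wear is listed at both ends, giving about 20 changes.
- GROUP2, baseline to week 12 (waitlist): wear is listed at week 12 but not at baseline, giving 0 changes.
- GROUP2, weeks 12 to 24 (intervention): wear is listed at both ends, giving about 20 changes.
- GROUP1, weeks 12 to 24 (maintenance, Section F): wear is listed at week 12 but not at week 24, giving 0 changes.

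**3. Consequence for each analysis.** The rank-sum test uses the first two lines: about 20 against 0. The sentence in Section G mentions only those randomized to the intervention, but a rank-sum test needs two samples, and the waitlist is the only comparator over that interval. The sizing SD uses the first and third lines: 20 + 20 = 40, fully supplied. Hypothesis 2 is a before-and-after comparison over those same windows and is also supplied.

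**4. Is the list complete?** Two things suggest it may not be. The general schedule includes baseline for everyone, and Section F expects GROUP1 activity data at 24 weeks that the list also omits. On the other side, the general schedule includes week 6, for which no wear is listed in either group, so it cannot by itself be read as a wear schedule. The documents do not settle the question.

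**5. Precision of an SD that covers both conditions.** For a normal outcome the 95% limits are the estimate multiplied by √(df/χ²), using the 97.5% and 2.5% points of chi-square.

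- Planned pooled intervention-window SD, n=40, df 39: 0.819 to 1.284.
- Within-group SD of baseline-to-12-week change over both groups, 20 + 20, df 38: 0.817 to 1.289.
- One group alone, n=20, df 19: 0.760 to 1.461.

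Sample size scales with the square of the SD. The planned SD therefore carries a range of 0.819² = 0.67 to 1.284² = 1.65 in the next trial's N from sampling error alone.

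**6. Illustration only.** The documents give no waitlist SD and no effect size. Assume a future two-arm trial with 80% power, two-sided alpha 0.05 and a difference of 0.5 intervention-period SDs. Then n per arm = 2(1.960 + 0.842)²/0.5² = 62.8, or 63. If the control-period SD is c times the intervention-period SD, the average variance is (1 + c²)/2.

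- c = 0.8: (1 + 0.64)/2 = 0.82, so 52 per arm; power at 63 per arm is 87%.
- c = 1.0: 63 per arm; power is 80%.
- c = 1.2: (1 + 1.44)/2 = 1.22, so 77 per arm; power at 63 per arm is 72%.

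The range 0.82 to 1.22 lies inside the sampling range 0.67 to 1.65 from step 5.

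**The case against.** The strongest reply is that Section D does not restrict wear to the listed dates. It describes the two ends of each Veteran's intervention window, while Section I, the opening of Section D and the test in Section G all place outcomes at baseline for everyone. The missing GROUP1 week-24 wear points the same way: the list may simply be short. This stands. A reader might infer that the pilot will certainly lack GROUP2 baseline step counts; the documents support only the conditional statement.

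A reader might also infer that the wear gap undermines the sizing SD. It does not, because that SD uses windows for which wear is listed at both ends.

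The choice of intervention-period change is stated openly, the control for the next trial is unspecified, and the waitlist includes six education sessions, so its SD need not match a future control arm. This also stands: leaving out a waitlist-period SD is a missed opportunity and not an error.

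Finally, a reader might infer that restricting to completers biases the SD. The completion wording does vary: Section C.1 has "retention (proportion of Veterans who complete program out of all enrolled", and the population section has "with the goal of having 40 Veterans complete the study (20% attrition rate". However, nothing says that Veterans who stop the program but are still measured will be excluded, or how many there would be. The documents support neither a size nor a direction of bias.

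What the reply does not remove is the conflict itself. The one passage that gives wear dates by group does not supply the data that the step-count comparison needs.

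**Conclusion.** The inconsistency is real and should be resolved. If the listed windows are followed, the between-group step-count comparison has about 20 changes in GROUP1 and none in GROUP2. The zero follows directly from the list; the 20 assumes equal attrition. Whether the list is what the team intends cannot be determined from the documents.

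The planned intervention-window SD and the before-and-after comparison in Hypothesis 2 are intact. For outcomes other than step count, the general schedule would supply GROUP2's baseline and week-12 values, so the gap is specific to the accelerometer.

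An SD of change that covers both conditions is worth adding because it costs almost no precision. The power figures of 87% and 72% rest on assumed SD ratios and show only why both arms matter. The definition of completing is a minor clarification.

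**What to change.** 1. Reconcile the wear list in Section D with Section I, the opening of Section D, Section F and Section G. Either list GROUP2 baseline wear, and GROUP1 week-24 wear if that is intended, or state in Section G that step count is not part of the between-group comparison. If GROUP2 baseline wear is not already planned, it costs at most one 10-day period for 25 Veterans. GROUP1 week-24 wear would be a separate addition. The second option costs one sentence but gives up the randomized comparison on the primary outcome.

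2. Beside the planned pooled SD, report the within-group SD of baseline-to-12-week change pooled over GROUP1 and GROUP2, with its 95% CI. This is one more table row per outcome, from assessments already scheduled. For step count it depends on GROUP2 baseline wear.

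3. State that the SDs include every Veteran with both measurements for the window, and define completing in one sentence.
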